## **Subjects selection criteria**

- **Inclusion Criteria**

- Age > 18 years
- Scheduled for surgery from an outpatient setting and scheduled for a pre-admission PAC appointment
- Risk stratification placing them in the top 25th percentile using our internally-validated PAC Risk Score.

- **Exclusion Criteria**

- Surgery on the day of admission (same-day surgery)
- Any upper extremity surgery

- **Sample Size**

- Our power analysis indicates that we need a total number of 150 patients to have at least 90% power in detecting a change in VS assuming a mean population VS (HR or BP) change of 12% from Phase 1 to Phase 2. We estimate a standard deviation of 10%, a type I error rate (2-sided) of 5%, and 1% missing follow-up data. We may have to consent up to 200 subjects in order to obtain the 150 evaluable subjects.
- We estimate this study lasting up to 12 months.

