**Objectives**

Using a portable, wireless multi-Vital Sign (VS) monitoring system developed by Caretaker Medical, we have several objectives:

- Primary:
  - Assess the feasibility of placing a Caretaker monitor on subjects scheduled for surgery for an 18-24 hour preoperative ambulatory monitoring session.
  - Assess the feasibility of placing a Caretaker monitor on subjects scheduled for surgery for the perioperative period defined as 18-24 hour intraoperative and postoperative ambulatory monitoring session.
  - Quantitate the data capture rate (estimated at over 99% in the company's prior studies) in this setting and how reliable our monitor return rate is in this setting.
- Secondary:
  - Assess the prevalence of alterations in VS (HR, RR, SaO2, BP, Cardiac Output, Stroke Volume, and HRV preoperatively) in a group of our highest acuity patients (top quartile of risk score) undergoing non-cardiac surgical procedures requiring at least a 2-day admission.
  - Assess any correlation of concerning ambulatory preoperative VS to postoperative VS.
    - We estimate that the percent of time the patient experiences these concerning preoperative VS values will correlate with a higher risk for a similar range of VS postoperatively, as well as undesired outcomes.
      - Undesired outcomes are defined as a) 30-day mortality, b) longer length of stay, c) higher ICU transfer, and 4) RRT calls).

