## **Methods and Measures**

### **Design**

The Caretaker device is a wrist device that has a version that has already been approved by the FDA for use amongst medical professionals. For the conduct of this protocol we propose to use a newer version of the device called VitalStream, which has been cleared for use by the FDA.

The New Caretaker device being used in the study has successfully passed all safety and accuracy tests by an independent lab, which have been submitted to the FDA already (see attached Declaration of Conformity).

We plan to monitor ambulatory preoperative CareTaker VS (HR, RR, SaO2, BP, Cardiac Output, Stroke Volume, and HRV) in random patients who meet our inclusion criteria for 18-24 hours, beginning during their preoperative (Preoperative Assessment Clinic, PAC) visit then overnight after they leave. Postoperatively, we will measure these VS in the same patients for approximately 24 hours postoperatively.

These monitors transmit VS to a data cloud, where we will be able to store and then later analyze the VS data. Clinical data will be collected from our EPIC Information System in order to provide pre- and postoperative information to examine corresponding risk factors and provide demographics.

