**Outcome Measure(s)**

- Primary outcomes:
  - Phase I: Quantitate the data capture rate and how reliable our monitor return rate is in this setting.
  - Phase 2: Quantitate the data capture rate in this setting for the perioperative period.
- Secondary:
  - Assess the prevalence of alterations in VS (HR, RR, SaO2, BP, Cardiac Output, Stroke Volume, and HRV preoperatively) in a group of our highest acuity patients (top quartile of our internal PAC risk score) undergoing non-cardiac surgical procedures requiring at least an overnight admission. See Table 2 for ranges.

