**Table 2. Data Sorted into Ranges for each parameter**

Heart rate (bpm)	Systolic Blood pressure (mmHg)	Diastolic Blood Pressure (mmHg)	RR (bpm)
<50	<90	<50	<8
51-70	91-100	51-65	9-12
71-90	101-120	65-80	13-16
91-100	121-140	81-90	17-20
101-110	141-160	91-100	21-25
>110	>160	>100	>25

- Assess any correlation of range data of ambulatory preoperative VS to postoperative VS.
- Determine if specific VS ranges are associated with undesired outcomes (defined as 1) 30-day mortality, 2) hospital length of stay, c) ICU transfer rate, and 4) Rapid Response Team calls).

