### **Analytical Plan**

- For the feasibility portion of the study, we will describe descriptive results of subjects' time of use of the monitor, their description of ease of use (difficult or easy), and the quantity of non-artifactual VS data.
- Results will be analyzed initially using descriptive statistics (percent of time VS remained in one of the ranges listed in Table 2) and means/standard error.
- We will compare relative incidence with matched cohort undergoing surgery using univariate analyses (categorical variables: chi-square test, continuous variables: Student's t-test or Mann-Whitney U test). We will use multivariable Cox proportional hazards regression modeling to assess VS risk factors associated with the postoperative undesired outcomes mentioned in outcome measures above.
- Statistical methods data will be expressed as mean  $\pm$  SD, number (percentage), odds ratio, and 95% CI. All P values will be two-tailed, and a P value less than 0.05 is considered significant.

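### The stated sample-size inputs call for about 10 to 33 patients by t-test, not 150, and the mean vital-sign change behind the figure is neither a listed outcome nor given a test

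*Combined protocol and SAP*

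**What the plan says.** Under Subjects selection criteria, the Sample Size bullet says "we need a total number of 150 patients to have at least 90% power in detecting a change in VS", where the change is a mean shift of 12% in heart rate or blood pressure from Phase 1 to Phase 2. It continues: "We estimate a standard deviation of 10%, a type I error rate (2-sided) of 5%, and 1% missing follow-up data". It then adds "We may have to consent up to 200 subjects in order to obtain the 150 evaluable subjects". It does not say whether the 10% is the SD of the within-patient change or of the measurements in one phase.

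Design makes the comparison within-patient: "Postoperatively, we will measure these VS in the same patients for approximately 24 hours postoperatively".

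The Phase I primary outcome is "Quantitate the data capture rate and how reliable our monitor return rate is in this setting", and the Phase 2 primary outcome is again data capture. The secondary outcomes, in Objectives, Outcome Measure(s) and the list after Table 2, are the prevalence of vital-sign alterations, the relation between the phases ("Assess any correlation of range data of ambulatory preoperative VS to postoperative VS") and associations with undesired outcomes.

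The Analytical Plan treats feasibility descriptively ("For the feasibility portion of the study, we will describe descriptive results of" monitor use, ease of use and usable data). It then gives percent of time in range and means, chi-square and Student's t or Mann-Whitney tests against a matched cohort, and Cox regression.

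**The concern.** The paragraph supplies every input to a standard power calculation except the meaning of the SD, so its result can be checked. A mean shift larger than its own SD is a very large standardised effect, and such effects need few patients. A stated need of 150 therefore suggests that an input is wrong or that the calculation belongs to another question.

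What is at stake is the justification for the number of high-risk surgical patients enrolled. A reader who tries to reproduce 150 cannot. The 12% figure also gives a misleading idea of what the study can detect. And the one comparison used to set the size does not reappear as an outcome or an analysis, so the plan never uses the power it claims.

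**Working it through.** **Inputs** (all from the Sample Size bullet, except the pairing, which is from Design): change 12%, SD 10%, two-sided alpha 0.05, power 0.90, missing 1%, same patients in both phases. Required n is the smallest n at which noncentral-t power reaches 0.90. The missing-data allowance is n/0.99, rounded up.

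**Can 150 be reproduced?** No, under any reading below.

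1. *Paired, 10% is the SD of the change.* Standardised effect d = 12/10 = 1.2. Normal approximation: n = ((1.960 + 1.282)/1.2)² = 7.3, so 8. Exact t: n = 9 gives power 0.882 and n = 10 gives 0.920. Need 10; 10/0.99 rounds up to 11.

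2. *Paired, 10% is the SD within one phase.* SD of the change = 10 × √(2(1 − ρ)), where ρ is the between-phase correlation.
   - ρ = 0: SD 14.14; n = 16 gives 0.887 and n = 17 gives 0.907. Need 17; 18 with missing data.
   - ρ = 0.25, 0.5, 0.75: need 14, 10 and 6.
   - Limiting case ρ = −1: SD 20; n = 31 gives 0.898 and n = 32 gives 0.908. Need 32.

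3. *Two independent groups* (not this design, but the least favourable standard reading). 15 per group gives 0.887 and 16 per group gives 0.907. Need 32 in total; 33 with missing data.

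4. *Rank test at its worst-case efficiency of 0.864.* 10/0.864 rounds up to 12 for reading 1; 32/0.864 rounds up to 38 for reading 3.

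5. *Stricter settings that the plan does not state.* Bonferroni over seven vital signs: 15 paired or 48 in two groups. 99.9% power: 20 paired or 74 in two groups.

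So 150 exceeds the t-test need by a factor between 150/33 = 4.5 and 150/10 = 15.

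**What would make 150 the right answer?** For a paired 12% change, the SD of the change would have to be about 45% (at SD 45%, n = 149 gives 0.899 and n = 150 gives 0.901). For two groups of 75, the SD would have to be about 22.5%. The protocol contains neither figure.

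**What 150 can detect with 90% power (paired).** The detectable standardised effect at n = 150 is 0.2664.
- 10% as SD of the change: 0.2664 × 10 = 2.66%.
- 10% as single-phase SD, ρ = 0: 0.2664 × 14.14 = 3.77%.

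At n = 148, after 1% missing, these are 2.68% and 3.79%, the same to one decimal.

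**Outcome and test.** Set beside the Sample Size bullet, the outcome lists contain rates, prevalences, correlations and associations, but no mean change between phases. The t and Mann-Whitney tests in the Analytical Plan belong to the matched-cohort comparison and are unpaired; the means with standard errors are descriptive. No Phase 1 versus Phase 2 test is named.

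**The case against.** The strongest reply is that the paragraph claims only a minimum of 90% power, and 150 patients deliver that with a wide margin. The primary outcomes are descriptive, so no primary inference depends on the calculation. This stands, and it limits the point to documentation. It does not rescue the sentence, which says that 150 are needed.

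The ceiling also depends on the test: 32 becomes 33 with the stated missing data, and a worst-case rank test would need about 38. That is correct, and still far from 150.

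The allowance to consent 200 does not help either. It explains the step from 150 evaluable to 200 consented, not the 150.

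A reader might infer more than the documents support:

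- *That the study is underpowered.* It is not, for the 12% change: every reading above reaches 90% power with far fewer than 150.
- *That enrolment should be cut to about 10.* The calculation concerns one mean change. The feasibility, prevalence and association aims are separate, and nothing here shows that 150 is too many for them.
- *That the lack of a precision statement for the feasibility rates is an error.* Those outcomes are planned as descriptive; a precision statement would be a matter of preference.
- *That range data should stay purely descriptive.* The plan uses descriptive statistics first, but it also intends to correlate range data between phases and relate vital-sign ranges to undesired outcomes.

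**Conclusion.** The concern holds as a fault in the stated basis for the sample size. The inputs as written require 10 patients (11 with 1% missing) if 10% is the SD of the change, at most 17 (18) if it is a single-phase SD with non-negative correlation, and 32 (33) in total even for independent groups. The mean change that set the size is neither a listed outcome nor given a test.

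The figures assume approximately normal data and a t-test, as is usual for such a calculation. The unstated meaning of the SD is covered by showing each reading; the conclusion does not depend on which one was intended. This should be fixed, but it threatens the transparency of the justification, not power or safety.

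**What to change.** Keep 150.

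1. Replace the power sentence. State whether 10% is the SD of the within-patient change or of a single phase, and correct it if it is mistaken. Then give the change detectable with 90% power at n = 150: about 2.7% if it is the SD of the change, up to about 3.8% if it is a single-phase SD with zero correlation.

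2. If the mean change stays the basis for size, list it as a secondary outcome and add a paired comparison of mean heart rate and blood pressure (paired t-test or Wilcoxon signed-rank). Before that, reconcile what Phase 2 covers: Objectives and Interventions and Interactions include intraoperative monitoring, whereas Setting has the monitor replaced in the PACU. The Phase 2 mean is undefined until those sections agree.

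3. Leave the planned range-data correlation and association analyses as they are.

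The cost is wording and a little analysis, with no extra patients, visits or data. The statement of 90% power for a 12% change is given up.

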## **Interventions and Interactions**

*The essential features of interventions and interactions used to generate data for the study should be described.*

- Each participant will have the study summary discussed with them, then allowed to read and sign the informed consent after having the chance to interact with the study equipment and ask questions. This will occur in the PAC prior to their preoperative visit.
- Participants who agree with entering the study will then have the CareTaker monitor placed on their left wrist and calibrated prior to them leaving the PAC.
- No surveys or questionnaires will be administered to subjects.
- An information sheet about the Caretaker device along with an emergency contact number will be given to the study subject at the time the device is placed.
- A description of the monitoring device is located in Appendix B.
- Phase I (preoperative phase) Participants will wear the CareTaker monitor for at least 12 hours (up to 24 hours) in their place of residence during the immediate time period after their initial monitor placement.
- The participants will be asked to remove the monitor and ship it back to us using pre-printed packaging or bring it with them on their day of surgery and admission to the hospital, whichever they prefer.
- For Phase II (intraoperative and postoperative phases) of the study, the participants will then have a monitor placed back on them for intraoperative and postoperative monitoring. The monitor will remain on them for up to 24 hours postoperatively, at which time a member of the research staff will remove the monitor.
- Thus, the total length of time participants will undergo active CareTaker monitoring will be 24-48 hours, divided between pre-and intra- and postoperative phases.
- Participants who complete the entire study will be compensated \$50 for their time and efforts.

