### **Setting**

The subjects will be recruited in the PAC, where their monitoring period will start, and will continue at their residence (or wherever they decide to stay that night). They will return the monitor with them into the holding area on the day of their surgical procedure. We will replace their monitor on them in the Post-Anesthesia Care Unit (PACU) where it will remain with the patient for 24 hours +/- 6 hours continuously monitoring.

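### Phase 1 and Phase 2 can cover different shares of night, so the all-hours secondary summaries mix day-night differences into the pre-to-post comparison; the stated wear times also conflict.

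*Combined protocol and SAP*

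**What the plan says.** The protocol states the length of each phase in several places, and the statements differ.

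**Phase 1 (preoperative)**
- Objectives: "for an 18-24 hour preoperative ambulatory monitoring session". Design also gives 18-24 hours.
- Interventions and Interactions: "Participants will wear the CareTaker monitor for at least 12 hours (up to 24 hours) in their place of residence".
- Clock coverage, Design: "beginning during their preoperative (Preoperative Assessment Clinic, PAC) visit then overnight after they leave". Table 1 places removal on the day after the clinic visit. No start or stop time is fixed.

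**Phase 2**
- Objectives: "defined as 18-24 hour intraoperative and postoperative ambulatory monitoring session".
- Design: "we will measure these VS in the same patients for approximately 24 hours postoperatively".
- Setting, counting from the recovery unit: "where it will remain with the patient for 24 hours +/- 6 hours continuously monitoring", that is, 18-30 hours.
- Interventions and Interactions: intraoperative monitoring is included, followed by up to 24 hours postoperatively, with no minimum.

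**Analysis**
- The Analytical Plan's descriptive summary is "percent of time VS remained in one of the ranges listed in Table 2", together with means.
- Sample Size is built on the pre-to-post change, "assuming a mean population VS (HR or BP) change of 12% from Phase 1 to Phase 2".
- The outcome list under Table 2 adds the correlation of preoperative with postoperative range data, and the association of ranges with undesired outcomes.
- No section aligns the data by clock hour, separates day from night or adjusts for time of day.

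**The concern.** Percent of time corrects for how long the monitor was worn, but not for which hours were worn. Phase 1 begins at a clinic appointment, and Phase 2 begins in theatre or the recovery unit. Two unrelated schedules therefore decide which clock hours each phase contains.

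If heart rate and blood pressure fall at night, a phase with a larger share of night hours has a lower mean and more time in the low Table 2 ranges, whatever surgery does. Two kinds of analysis are exposed:

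- **Within patient:** the Phase 1 to Phase 2 change and the pre-to-post correlation.
- **Between patients:** the preoperative exposure that is related to mortality, length of stay, ICU transfer and rapid response calls. It would vary partly with the hour at which each patient started and stopped wearing the device.

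Where some descriptions of Phase 2 include intraoperative hours and others do not, a second kind of non-comparable time enters the same contrast.

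**Working it through.** **The plan's own figure.** Sample Size gives 150 patients for a 12% change, SD 10%, two-sided 5% and 90% power. Read as a paired change, n = ((1.960 + 1.282) × 10/12)² = 7.3, so 8 patients. The 150 is not reproduced from those inputs. That is a separate matter, and nothing below depends on it. It does give a scale: with 150 pairs and SD 10%, the change detectable at 90% power is (1.960 + 1.282) × 10/√150 = 2.65%.

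**Inputs.** From the protocol: the phase lengths above, an overnight Phase 1, and removal the day after the clinic visit. Assumed, not in the protocol: 8 night hours (22:00-06:00), all within Phase 1; a night fall d of 10-20% of the waking level, the same at home and in hospital; no effect of surgery.

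**Formula.** With night share s, a phase mean is 1 − d × s in units of the waking level. The spurious change, Phase 2 minus Phase 1, is d × (s1 − s2). For a 24-hour Phase 2, s2 = 8/24 = 0.333.

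| Phase 1 length | s1 | s1 − s2 | Spurious rise, d = 10-20% (points) | Share of the planned 12% |
|---|---|---|---|---|
| 24 h | 0.333 | 0 | 0 | 0 |
| 21 h | 0.381 | 0.048 | 0.5-1.0 | 4-8% |
| 18 h | 0.444 | 0.111 | 1.1-2.2 | 9-19% |
| 15 h | 0.533 | 0.200 | 2.0-4.0 | 17-33% |
| 12 h | 0.667 | 0.333 | 3.3-6.7 (bound) | 28-56% |

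Expressed relative to the Phase 1 mean, the figures are slightly larger: 1.2-2.4% at 18 hours and 3.6-7.7% at 12 hours.

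**Phase 2 other than 24 hours.** An 18-hour Phase 2 with 8 night hours has s2 = 0.444. Against an 18-hour Phase 1 the difference is zero. Against a 21-hour Phase 1 it is (0.381 − 0.444) × 10-20% = −0.6 to −1.3 points, so the sign reverses. A 30-hour Phase 2 holding 8 night hours has s2 = 0.267. Against an 18-hour Phase 1 it gives (0.444 − 0.267) × 10-20% = +1.8 to +3.6 points.

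**Percent of time.** Take, for illustration, a range occupied during 60% of sleep and 20% of waking time. The reading is 0.6 × s + 0.2 × (1 − s): 33% over 24 hours, 38% over 18, 41% over 15 and 47% over 12, with no difference in physiology.

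**Consequence for a test.** Suppose every patient wore the monitor from 14:00 to 06:00 in Phase 1 (16 hours, s1 = 0.50). The shared shift is (0.50 − 0.333) × 10-20% = 1.7-3.3 points. A two-sided 5% test on 150 pairs with SD 10% would reject about 53% of the time at 1.67 points and about 98% at 3.33, with no effect of surgery. This is a hypothetical common shift. In practice the mean shift is an average over patients' start and stop times.

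**The case against.** Several points on the other side stand.

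- **A stronger reading is tempting, and the protocol does not support it.** From the 12-hour minimum a reader might infer that Phase 1 could contain no night at all, giving a bias of 3.3-6.7 points in either direction. Design says monitoring continues overnight, and Table 1 puts removal on the following day, so a window without night hours is not the planned schedule.
- **The 12-hour upper bound is barely attainable.** Eight night hours in a 12-hour window need a start at about 18:00 or later. The 12 hours are also counted at the residence, so clinic time comes on top.
- **The 28-56% is not an expected bias.** It sets one patient's worst case against a population mean change.
- **Short wear is not distorting in itself.** A 12-hour window from 14:00 to 02:00 has 4/12 = 33% night, the same as a full day. A reader might suppose that early stoppers are always the most distorted, but clock position matters as well as duration.
- **Objectives and Design already give 18-24 hours for Phase 1.** If that range applies, the figure under these assumptions is at most 1.1-2.2 points against a 24-hour Phase 2.
- **The affected analyses are secondary.** The Analytical Plan names no test of the mean Phase 1 to Phase 2 change; that quantity appears only in Sample Size.

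These points limit the size of the problem but do not remove it. If Phase 1 contains the whole night and is shorter than 24 hours, its night share is always above one third. Against a 24-hour Phase 2, those errors push the same way and do not cancel across patients.

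**Conclusion.** The concern holds as a modest, avoidable bias in secondary analyses, together with an internal contradiction on wear times in both phases.

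Under the assumptions stated, the spurious rise is about 0.5 to 4.0 points for Phase 1 lengths of 21 down to 15 hours, with 3.3-6.7 only as an upper bound at 12 hours. It is zero if both phases run a full 24 hours. A Phase 2 shorter than 24 hours can reduce or reverse it. Size and direction rest on the night fall, the night hours and the start times, none of which the protocol gives.

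A reader might infer that the trial's main results are compromised. They are not: the primary outcomes are data capture and monitor return, and day-night mix does not bias them. Nor may Phase 2 be taken as purely postoperative, since Objectives and Interventions and Interactions both include intraoperative time.

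**What to change.** 1. Reconcile the wear times in Objectives, Design, Setting, and Interventions and Interactions, so that each phase has one stated window, including whether Phase 2 contains intraoperative hours.
2. In the Analytical Plan, report the means and the percent of time in each Table 2 range separately for day and night in each phase, with the clock boundaries stated in advance. Use these day and night values in the pre-to-post correlation and in the outcome models. Matching hours within a patient does not by itself equalise night share between patients, so this step is needed as well as the next.
3. Compute the Phase 1 to Phase 2 change on clock hours present in both phases of each patient, with intraoperative hours excluded or shown separately.
4. Keep the all-hours version as a sensitivity analysis.

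**Cost.** This is a change of wording in the protocol and analysis plan; no extra patients, visits or measurements are needed. Unmatched hours drop out of the matched comparison, and these may include early postoperative hours. With Phase 1 from 14:00 to 07:00 and placement in the recovery unit at 10:00, for example, the first four postoperative hours would be lost, so they should still appear in the all-hours result. The approach needs time-stamped records. That is a reasonable inference from continuous transmission to a data store, but the protocol does not state it, and it should be confirmed.
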